4 BACKGROUND AND RATIONALE

Atrial fibrillation (AF) is the most common sustained arrhythmia in man, and has an increasing population prevalence over time. Treatment is aimed at stroke prevention on the one hand, and amelioration of symptoms (palpitations, lightheadedness, dyspnea, fatigue) due to the arrhythmia. Medical therapy often fails to render a satisfactory response for the latter, prompting the search for alternative therapies. Surgical and, in the last 15 years, catheter ablation techniques have been devised to try to prevent episodes from starting. Groundbreaking work by Haïssaguerre¹ showed that premature discharges or rapid repeated firing from the pulmonary veins (PVs) could trigger AF episodes and that electrical isolation of the PVs could potentially cure the patient of AF. PV isolation currently is a painstaking process consisting of delivering radiofrequency energy in the left atrium to isolate these veins. Such procedures take 3-5 hrs. to complete depending on the complexity of the individual case, and a majority of patients require a 2nd or even 3rd procedure to achieve acceptable antiarrhythmic results. Despite considerable investigative effort, the exact pathophysiology of how PV triggers initiate and or maintain episodes of AF has been elusive.

Recently, Narayan et al² have developed an algorithm that has been licensed for use with a novel mapping technology (RhythmView, Abbott (Topera, Inc.), Menlo Park, CA) for analyzing atrial recordings during human AF, finding that >95% of cases demonstrate either a rapidly spinning rotor (small circuit) or very rapid focal impulse formation. Furthermore, they have shown that catheter ablation at these relatively circumscribed areas can significantly affect AF, either by substantial slowing of the rate or termination (to an atrial tachycardia or sinus rhythm). In the CONFIRM (CONventional vs Focal Impulse and Rotor Modulation) trial, patients were treated with either conventional mapping and ablation (largely PV isolation or PVI) vs ablation of rotors or sites of focal impulse formation as designated by the mapping algorithm, followed by conventional ablation (PVI). The authors found much higher acute and long-term efficacy when focal impulse and rotor modulation (FIRM procedure) was used (82.4 vs 44% freedom from AF at 24 months post procedure). Although CONFIRM was a controlled study, a randomized evaluation would be warranted.

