6.2 RANDOMIZATION

Block randomization using a web-based database system will be used to assign subjects (1:1) to the conventional AF ablation treatment without FIRM-guided diagnostic procedure, or to the FIRM-guided procedure followed by conventional AF ablation.

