10.2 STUDY PROCEDURE

The subject will be scheduled to undergo study treatment after the subject has met all inclusion and exclusion criteria, has signed the study informed consent form, and has completed the baseline assessments. Once enrolled in the study, the subject will be randomized to undergo either conventional AF treatment with ablation, or FIRM-guided procedure followed by conventional AF ablation.

A. *Pre-procedure Preparation*

Just prior to and/or during the procedure, a glycoprotein IIb/IIIa inhibitor or other platelet inhibitor may be administered if it is standard practice. The insertion of the FIRMap catheter or performing transseptal puncture, whichever comes first, will be followed immediately by an IV heparin bolus, followed by repeated heparin administration, adjusted as necessary to achieve and maintain an ACT above 300 seconds.

B. *Intra-procedure Guidelines*

During the procedure, the following actions should be taken and appropriate data collected. Table 6.

Table 6 – Intra-Procedure Guidelines

Parameter	Description
Vascular access	Under sterile technique, the right and/or left femoral veins may be cannulated via Seldinger, or percutaneous approach. Other vascular access also may be obtained based upon physician judgment.
Reference catheter placement	Reference catheters (including 64-pole FIRMap catheter(s)) may be inserted and placed within the heart to record signals as clinically required at the discretion of the physician.
Access to left atrium	Access to the left atrium should be according to the institution's standard practice.
Anticoagulation	Upon insertion of 64-pole FIRMap catheter or transseptal puncture (whichever comes first), an IV heparin bolus should be administered, followed by repeated heparin administration, adjusted as necessary to achieve and maintain an ACT above 300 sec.
Catheter placement	Catheters may be inserted and used according to the institution's standard practice.
Source arrhythmia diagnosis	After obtaining at least 1 minute of continuous electrograms from the 64-pole FIRMap catheter either simultaneously or sequentially in the right and left atria, these electrogram data will be transferred to the Topera RhythmView® system. This will then produce FIRMap displays which will be interpreted by the operator to determine which locations have focal or rotor rhythms that could be sources of the AF.

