3-D Electroanatomic Mapping	3-D electroanatomic maps may be created using CARTO (Biosense Webster, Johnson & Johnson) or Nav-X (St. Jude Medical) systems for documentation of anatomy and ablation lesion locations.
Induction of sustained AF	If the patient is not experiencing spontaneous, sustained AF (>5 min uninterrupted), induce sustained AF by atrial burst pacing, typically from the coronary sinus, with or without isoproterenol infusion in conventional clinical fashion. IF AF CANNOT BE SUSTAINED, THE PATIENT DOES NOT MEET THE INCLUSION CRITERIA FOR THE PROTOCOL AND THE PATIENT WILL UNDERGO CONVENTIONAL AF ABLATION PER PHYSICIAN DISCRETION.

Ablation data	For each ablation, the following data will be recorded: time, catheter size, lesion number, phrenic nerve assessment (if in an area of potential phrenic nerve proximity), approximate catheter tip location, duration of application, average temperature, and any comments.
FIRM-guided procedure	Under fluoroscopic guidance, a cardiac ablation catheter is passed to the location(s) identified as AF source rhythms (rotors or focal impulses). Therapy can be applied at up to 6 sites identified by the initial or repeated FIRMap per standard practice.
Conventional Ablation	Conventional ablation typically consists of isolation of all four pulmonary veins per guidelines. In addition, in the conventional arm of the study, data will be recorded regarding any additional ablation such as that performed per local routine for AF (e.g. CFAE, roof line, additional trigger elimination, etc.). Such additional ablation is NOT typically performed in the FIRM-guided limb where only PVI is typically performed for the purposes of AF ablation beyond FIRM-guided locations.
Additional ablation for other arrhythmias (non-AF)	Additional ablation for other arrhythmias will be noted for atrial tachycardia (AT) and/or right cavo-tricuspid isthmus ablation in the event that the patient has documented AT/atrial flutter prior to or during the procedure.
Electrograms	Electrogram recordings evaluating conduction into or out of each treated vein.

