- Post procedure rhythm monitoring will occur either via a Cardiac Implanted Electronic Device (CIED) with interrogation at intervals per protocol or all subjects without CIED will receive a 24 – 72 hour Holter monitor at 1, 3, 6, and 12 months post-procedure. If AF symptoms are documented as recurrent AF within the follow-up period, further treatment shall be at the discretion of the physician (e.g., drugs, re-ablation, etc.).
- Pre-discharge evaluation will include:
 - Diagnostic 12-lead ECG
 - Symptom and rhythm assessment
 - Antiarrhythmic medications
 - Adverse events

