This endpoint will be evaluated using a Chi-Square test of independence, the proportions assumed to be binomial for each group.

C. Acute Safety (Primary safety endpoint)

The acute safety success of either treatment arm is defined as freedom from serious adverse events related to the procedure within ten (10) days of the index procedure. The proportion of successes in each arm will be calculated as follows:

$$\frac{n}{N}$$

Where:

n = the total count of subjects presenting freedom from serious adverse events related to the procedure within ten (10) days of the index procedure.

N = the total count of subjects in that arm in the ITT group

The statistical hypothesis for this endpoint is operationalized as follows:

$H_0: p_E = p_C$

$H_A: p_E \neq p_C$

Where:

p_E = the proportion of "successes" in the FIRM arm

p_C = the proportion of "successes" in the conventional ablation control arm

This endpoint will be evaluated using a Chi-Square test of independence, the proportions assumed to be binomial for each group.

D. Long-Term Safety (Primary safety endpoint)

Long-term safety is defined as freedom from procedure-related serious adverse events (SAEs) (including those related to repeat procedures) within one year of the initial procedure.

The statistical hypothesis for this endpoint is operationalized as follows:

$H_0: p_E = p_C$

$H_A: p_E \neq p_C$

$\alpha =$

Where:

p_E = the proportion of subjects free from serious adverse events related to the procedure (including from any repeat procedures required) within one year of the index procedure in the FIRM arm

p_C = the proportion of subjects free from serious adverse events related to the procedure (including from any repeat procedures required) within one year of the index procedure in the conventional ablation control arm

The proportion of events in each treatment arm shall be evaluated relative to their respective primary endpoint using both Chi-Square (Binomial, 1df) and by Kaplan-Meier survival estimation. Each evaluation will include 95% confidence intervals.

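### Table 6 and Section 16.2.B conflict with Section 6.2 on FIRMap use in controls, and FIRM use at repeat procedures is neither addressed nor recorded although their SAEs count in one-year primary safety

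*Protocol*

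**What the plan says.** **Index procedure.** Section 6.2 randomises subjects "to the conventional AF ablation treatment without FIRM-guided diagnostic procedure, or to the FIRM-guided procedure followed by conventional AF ablation". Table 6 in Section 10.2 sets out the study procedure for both arms. Its reference-catheter row reads "Reference catheters (including 64-pole FIRMap catheter(s)) may be inserted and placed within the heart to record signals as clinically required at the discretion" (the physician's). Its source-diagnosis row has FIRMap electrograms sent to RhythmView and continues: "This will then produce FIRMap displays which will be interpreted by the operator to determine which locations have focal or rotor rhythms". Neither row names an arm. The conventional-ablation row does: "in the conventional arm of the study, data will be recorded regarding any additional ablation such as that performed per local routine for AF". Section 16.2.B defines acute success by FIRMap, and then plans a success proportion in each arm over that arm's ITT count and a chi-square test between arms.

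**Repeat procedures.** For documented recurrence, Section 10.2.D says "further treatment shall be at the discretion of the physician (e.g., drugs, re-ablation, etc.)". No technique is named for either arm. Under Section 10.3, re-ablation makes the subject a primary effectiveness failure.

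**Safety.** Long-term safety, a primary endpoint in Sections 7.1 and 16.2.D, is "freedom from procedure-related serious adverse events (SAEs) (including those related to repeat procedures) within one year of the initial procedure". It is compared by randomised arm with a null hypothesis of equal proportions.

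**The concern.** The comparison is FIRM plus conventional ablation against conventional ablation. If the tested technology can be used in controls, the contrast weakens, and the protocol leaves this unsettled in two places.

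At the index procedure, an investigator who places the FIRMap catheter in a control follows Table 6 and departs from 6.2. Section 13.4 cannot settle whether that is a deviation while both texts stand.

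At a repeat procedure there is no text to apply. Section 9.1 requires investigators to be trained in FIRM and to have taken part in 5 FIRM-guided procedures, and Section 9.2 requires every site to have the catheter and the mapping system. FIRM-guided repeats in controls are therefore foreseeable. Any SAE they cause would count in the control arm of a primary safety endpoint. Because that endpoint is tested for equality with no margin stated, a diluted difference makes a non-significant result more likely, and such a result can be misread as reassurance.

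**Working it through.** **1. The index-procedure passages side by side**

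- Section 6.2: no FIRM-guided diagnostic procedure in controls.
- Table 6, reference-catheter row: FIRMap catheter at physician discretion, any subject.
- Table 6, source-diagnosis row: FIRMap recording and interpretation, any subject.
- Section 16.2.B: both routes to acute success need FIRMap. One asks whether the source has gone from the map; the other looks at electrogram amplitude in a region the map designated.

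If 6.2 is followed, a control has no mapped source, so the control proportion in 16.2.B is undefined, or zero by construction, and the planned test tells us nothing. If 16.2.B is to be carried out as written, controls must be mapped, which 6.2 excludes. Both cannot stand.

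**2. Repeat procedures and one-year safety**

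The protocol states no rate for this point, and its alpha and Section 16.4 are redacted, so there is no figure to reproduce. The calculation below gives scale only.

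- From the protocol: up to 350 subjects, 1:1, so 350 / 2 = 175 per arm.
- Assumed: control SAE risk c = 5%; excess risk from FIRM d = 5 points; two-sided alpha 0.05.
- Unknown, varied: r, the share of controls re-ablated within the year; f, the share of those repeats that are FIRM-guided.

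The model gives each FIRM-guided repeat in a control the same excess d and ignores further FIRM exposure at repeats in the FIRM arm:

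- FIRM arm risk = c + d = 10%
- control risk = c + r·f·d
- difference = d·(1 − r·f)
- controls with a FIRM-guided repeat = 175·r·f
- added control events = 175·r·f·d

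Power is the normal approximation for two proportions, with the pooled standard error under the null.

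| r | f | r·f | Controls with FIRM repeat | Added control events | Difference (points) | Power |
|---|---|---|---|---|---|---|
| – | – | 0 | 0 | 0 | 5.0 | 43% |
| 10% | 25% | 2.5% | 4.4 | 0.2 | 4.9 | 41% |
| 20% | 50% | 10% | 17.5 | 0.9 | 4.5 | 35% |
| 30% | 100% | 30% | 52.5 | 2.6 | 3.5 | 22% |

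For the middle row: 0.20 × 0.50 = 0.10; 5.0 × 0.90 = 4.5 points; 175 × 0.10 × 0.05 = 0.9 events. Even without dilution, power for this assumed difference is only 43%.

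**3. Primary effectiveness**

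The endpoint is single-procedure freedom from recurrence and re-ablation counts as failure, so r and f do not enter it. Only FIRM-guided ablation in a control at the index procedure could dilute it. If a share x of controls received that, with assumed success of 65% against 50%, the control rate would be 50% + x × 15 points. At x = 10% the difference is 13.5 points and power falls from 81% to 73%. At x = 20% it is 12 points and 63%. Table 6 does not authorise such ablation in controls, so these figures show only what an unclear rule puts at risk.

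**The case against.** A reader might infer that FIRM is simply not kept out of the control arm. The protocol does not support that. Section 6.2 excludes the FIRM-guided diagnostic procedure in controls. The Table 6 row permits recording signals, not FIRM-guided ablation, and the table has separate rows for FIRM-guided and conventional ablation. Its examples of additional control-arm ablation do not include FIRM. The index-procedure defect is a contradiction, not a missing rule.

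A reader might also infer that control re-ablations are allowed to be FIRM-guided. That rests on silence: nothing allows it and nothing bars it. The background remark that "a majority of patients require a 2nd or even 3rd procedure" gives no time frame, so it cannot supply a one-year rate.

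Several safeguards stand:

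- Re-ablation is a primary effectiveness failure.
- Acute safety is a separate primary endpoint covering the first 10 days and is largely free of repeats.
- Table 7 records the catheters and mapping equipment used at the study procedure.
- Table 5 collects repeat ablations, and Table 4 compares descriptive information on them.
- Counting SAEs by randomised arm follows intention to treat and is not an error.
- Table 4 means cumulative freedom from AF to include repeat-ablation results.

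Supportive analyses may be in the statistical analysis plan, which is not shown, so their absence from the protocol is no finding.

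These points narrow the concern but do not remove it. None reconciles 6.2 with Table 6 and 16.2.B. The acute endpoint cannot show later harm, and no listed item states that technique at a repeat is captured.

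**Conclusion.** The contradiction among Sections 6.2, 10.2 (Table 6) and 16.2.B is certain from the text and needs no assumption.

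The gap at repeat procedures is also real, but its effect is conditional. It matters for one-year safety only if controls receive FIRM-guided repeats and FIRM changes risk. If FIRM adds risk, the direction is toward no difference. The size is about r × f of the true difference: 2.5% at the low end of the assumed values, 10% in the middle and 30% if three in ten controls are re-ablated and every repeat is FIRM-guided. The document fixes neither r nor f. At the low and middle values fewer than one extra control event is expected, so a claim that a FIRM risk would be hidden goes too far.

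Primary effectiveness is not affected by repeats. The point is a modest, inexpensive improvement; it does not show that the primary comparison is invalid.

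**What to change.** 1. Reconcile Table 6 and Section 16.2.B with Section 6.2. Mark which Table 6 rows apply to which arm. If 6.2 stands, list index-procedure FIRMap use in a control as a recorded deviation, and recast the acute endpoint so that it does not need FIRMap data from controls.
2. State in the protocol how FIRM use at repeat procedures is treated for data collection, and record on the eCRF, for every repeat in both arms, whether FIRM mapping or FIRM-guided ablation was used.
3. Keep the intention-to-treat one-year safety analysis as primary. Beside it, report procedure-related SAEs of the index procedure alone, in the same way for both arms, with the number of FIRM-guided repeats by arm.

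Two tempting additions should be avoided. Censoring only controls at first FIRM use is informative, because repeats follow recurrence, and it is one-sided. Counting FIRM-guided repeats as failures only in controls tilts the cumulative outcomes toward FIRM. How recurrence is treated remains a clinical matter, and no rule on it is proposed here.

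Cost: wording in two sections, one eCRF field and one supportive table. The field must be collected prospectively, since technique may not be fully recoverable later.

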3 PROTOCOL SYNOPSIS

Sponsor: Abbott Electrophysiology (Topera, Inc.)

Protocol Title: Randomized Evaluation of Atrial Fibrillation Treatment with Focal Impulse and Rotor Modulation Guided Procedures (REAFFIRM)

Planned Study Centers: Up to 25 centers in Europe and North America

Primary Objective:

Evaluate the safety and effectiveness of FIRM-guided procedures in addition to conventional ablation for the treatment of patients with de novo persistent atrial fibrillation (AF).

Secondary Objectives:

- Evaluate the acute effectiveness of FIRM-guided procedures in eliminating the source of arrhythmia.

Study Design:

This is a prospective, multicenter, randomized study to assess the safety and effectiveness of FIRM-guided procedures followed by conventional ablation including PVI versus a standard PVI procedure for the treatment of de novo persistent atrial fibrillation.

Sample Size:

A total of up to 350 subjects will be enrolled and equally (1:1) randomized between those undergoing conventional AF treatment with ablation, vs. those with FIRM-guided procedures followed by conventional AF ablation. Additionally, ablation of any atrial tachycardias (AT) and/or the cavotricuspid isthmus may be performed in those subjects with documented AT/atrial flutter.

Study Duration:

Subject participation will require up to 13 months. The follow-up assessments will occur at 7-10 days post-procedure, 1, 3, 6, and 12 months post-procedure.

Inclusion Criteria:

Subjects are required to meet the following inclusion criteria:

1. Male or female 18 – 80 years of age.
2. Experiencing at least two (2) documented episodes of persistent atrial fibrillation (including long standing persistent) during the 3 months preceding study entry with clinical indication for AF ablation per guidelines. At least one episode must be documented by rhythm strip or ECG.
3. Refractory, contraindicated, or intolerant to Class I or III anti-arrhythmic medications. Drug doses must be therapeutic and stable.
4. Oral anticoagulation required with either Novel Oral Anticoagulant (e.g. dabigatran, rivaroxaban, apixaban), Warfarin (therapeutic INR ≥ 2.0 for at least three weeks prior to randomization), or other similar standard-of-care oral anticoagulant therapy is required (aspirin is not considered similar) for those subjects who meet two or more of the following criteria:
 - a. Age 65 years or older
 - b. Diabetes
 - c. Coronary artery disease (CAD)
 - d. Congestive heart failure

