¹ Haïssaguerre M, Jaïs P, Shah DC et al. Spontaneous initiation of atrial fibrillation by ectopic beats originating in the pulmonary veins. *N Engl J Med* 1998; 339: 659–66.

² Narayan, S.M., D.E. Krummen, P. Clopton, K. Shivkumar and J.M. Miller. Direct Or Coincidental Elimination of Stable Rotors or Focal Sources May Explain Successful Atrial Fibrillation Ablation: On-Treatment Analysis of the CONFIRM (CONventional ablation for AF with or without Focal Impulse and Rotor Modulation) Trial. *Journal of the American College of Cardiology* (2013) 62:138-147.

REAFFIRM is a prospective, multicenter, randomized, controlled study to assess the safety and effectiveness of FIRM procedures followed by conventional ablation including PVI versus a standard conventional procedure including PVI for the treatment of persistent atrial fibrillation.

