4.2 HYPOTHESIS

Focal Impulse and Rotor Modulation (FIRM) guided procedures will eliminate the source of clinical arrhythmias in subjects with indications for AF ablation procedures.

5 **STUDY OBJECTIVES**

The primary objective is to evaluate the safety and effectiveness of FIRM procedures in addition to conventional ablation for the treatment of persistent atrial fibrillation (AF).

The secondary objectives are: 1) to evaluate the acute success of FIRM-guided procedure in eliminating the source of arrhythmias, and 2) to evaluate quality of life outcomes.

6 **STUDY DESIGN**

The study is designed as a prospective, multicenter, randomized study to assess the safety and effectiveness of FIRM procedures followed by conventional ablation including PVI versus a standard PVI procedure for the treatment of de novo persistent atrial fibrillation.

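### The objective is FIRM added to conventional ablation, but Table 6 lets the conventional component differ by arm, so the contrast is in part a comparison of two strategies

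*Protocol*

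**What the plan says.** Section 5 (Study Objectives) sets the primary objective as "FIRM procedures in addition to conventional ablation for the treatment of persistent atrial fibrillation". The Synopsis says the same in substance. Section 10.2 describes subjects as "randomized to undergo either conventional AF treatment with ablation, or FIRM-guided procedure followed by conventional AF ablation", and Sections 6.1 and 6.2 define the arms likewise. Read plainly, both arms get the same conventional component and one also gets FIRM.

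The comparator is described in three ways:

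- The Synopsis (Study Design) has "FIRM-guided procedures followed by conventional ablation including PVI versus a standard PVI procedure", and Section 6 repeats it.
- Section 4 (Background and Rationale) has "versus a standard conventional procedure including PVI for the treatment of persistent atrial fibrillation".
- Table 6 in Section 10.2, row on conventional ablation, describes isolation of the four pulmonary veins as the typical content. It then says that "in the conventional arm of the study, data will be recorded regarding any additional ablation", giving CFAE, a roof line and additional trigger elimination as examples of local routine.

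The same row then says of the FIRM arm: "Such additional ablation is NOT typically performed in the FIRM-guided limb where only PVI is typically performed for the purposes of AF ablation", apart from the FIRM-guided sites themselves.

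The row on ablation data in Table 6 asks for time, lesion number, approximate tip location and duration for every ablation, with no restriction by arm.

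**The concern.** An add-on question needs the background treatment to be the same in both arms. Table 6 describes a background that tends to differ: allocation to FIRM adds FIRM and may also reduce other AF lesions. A difference between arms would then carry both effects, while the objective credits it to FIRM alone.

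Safety is affected as well as effectiveness. Both primary safety endpoints (Section 7.1) count procedure-related serious adverse events. Section 4.1 itself links the number of lesions to left atrial damage, and longer procedures to complications. The comparison of total RF ablation time in Table 4 has the same ambiguity.

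At stake is what the trial may conclude. A reader who takes the objective at its word would report an add-on effect from a contrast that may not be one.

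**Working it through.** **Step 1: the texts side by side.**

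| Place | FIRM arm | Control arm |
|---|---|---|
| Sections 5, 6.1, 6.2, 10.2 (text) | FIRM, then conventional ablation | Conventional ablation |
| Synopsis (Study Design), Section 6 | FIRM, then conventional ablation including PVI | Standard PVI |
| Section 4 | FIRM, then conventional ablation including PVI | Conventional procedure including PVI |
| Table 6 | FIRM sites, then typically PVI only | Typically PVI, plus any extra AF ablation by local routine |

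Only the first row gives the objective's contrast without qualification. The second gives it only if conventional ablation means PVI and nothing more. The third leaves the content of the comparator open. The fourth lets the background differ by arm. Ablation for documented AT or flutter is allowed in either arm (Section 6.1) and is not part of the problem.

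**Step 2: what the contrast contains.** Let s_C and s_F be the shares of control and FIRM subjects given non-PVI AF lesions, and d the change in the success proportion that those lesions cause in those who receive them. If d is the same in both arms:

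observed difference = add-on effect of FIRM − (s_C − s_F) × d

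The second term vanishes if s_C = s_F or if d = 0. If d is positive, the difference understates the add-on effect. If d is negative, it overstates it. The protocol gives none of s_C, s_F or d.

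**Step 3: scale, by assumption only.** There is no figure of the plan to reproduce: alpha and the power section (16.4) are blacked out. The one input from the document is up to 350 subjects at 1:1, that is 350 / 2 = 175 per arm. Assumed: 60% success (within the 50–70% that Section 4.1 cites for freedom from symptoms), s_F = 0, and d = 10 points in either direction.

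Standard error of the difference = sqrt(2 × 0.6 × 0.4 / 175) = 0.052, or 5.2 points.

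| s_C | Shift = s_C × 10 points | In standard errors |
|---|---|---|
| 25% | 2.5 | 2.5 / 5.2 = 0.5 |
| 50% | 5.0 | 5.0 / 5.2 = 1.0 |
| 75% | 7.5 | 7.5 / 5.2 = 1.4 |

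Taking s_F as zero gives the largest shift for each s_C, as long as s_F does not exceed s_C. With s_C = 50% and s_F = 25%, the shift is (0.50 − 0.25) × 10 = 2.5 points.

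**Step 4: the same scale as power, by assumption only.** Take two-sided alpha 0.05, 60% success in controls given PVI only, a true add-on gain of 15 points (75% in the FIRM arm), beneficial extra lesions (d = +10 points) and s_F = 0. Power is from the normal approximation for two proportions, with pooled variance under the null.

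| s_C | Control success | Difference | Power |
|---|---|---|---|
| 0% | 60.0% | 15.0 points | 85% |
| 25% | 62.5% | 12.5 points | 72% |
| 50% | 65.0% | 10.0 points | 53% |
| 75% | 67.5% | 7.5 points | 34% |

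At alpha 0.025, the first and third rows become 78% and 42%.

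**Step 5: could the recorded lesions repair it afterwards?** Not fully. Extra lesions are delivered after randomization and chosen by the operator. Adjusting for them, or selecting subjects on them, does not restore the randomized add-on comparison.

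**The case against.** The best reply is that the wording in Table 6 describes practice. It says what is typical; it sets no rule and bars nothing in the FIRM arm. PVI is the core of treatment in both arms. Comparison with usual care is also a legitimate randomized design, and Sections 4, 6.1, 6.2 and 10.2 can be read that way. All of this stands. It means that the contrast is valid as a comparison of strategies, and that controls treated with PVI only still inform the intended add-on contrast. It does not reconcile the objective with Table 6: if usual care is the comparator and FIRM subjects typically get less of it, the objective should say so.

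A second reply is that the figures above have no source in the document. That is correct, and they show scale only.

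A third is that the statistical analysis plan may deal with this. It may hold supportive analyses, and their absence from the protocol is no fault. But the conflict lies between the objective and the treatment definition, both of which the protocol fixes.

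A reader might also infer from Table 6 that extra lesions are recorded in the control arm only. The document does not support this. The ablation-data row covers each ablation without naming an arm, and Table 7 notes total RF time in both groups. What is lacking is an explicit lesion-type label for non-PVI AF ablation in the FIRM arm.

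**Conclusion.** The concern holds in a limited form. The objective, the design statement and Table 6 do not describe one and the same comparison. To the extent that extra AF lesions are given to controls and not to FIRM subjects, the trial compares FIRM plus PVI with conventional ablation by local routine, for effectiveness and for safety.

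It would be tempting to go further and say that the trial does not test FIRM as an add-on at all. The document does not support that. Nothing prohibits extra lesions in the FIRM arm, their frequency among controls is not stated, and with equal use in both arms the contrast would be the intended one.

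Neither the size nor the direction of the departure can be derived. The shift of 2.5 to 7.5 points rests entirely on an assumed 10-point effect, assumed shares of 25% to 75% and no extra lesions in the FIRM arm. No size is offered for safety. The point should be settled because it decides what the trial may conclude and costs little.

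**What to change.** 1. Reconcile the Synopsis, Sections 4, 5 and 6, and Table 6, so that each describes the same comparator and the same conventional component per arm. Which clinical rule on additional ablation is right is not for this review.
2. If Table 6 stands, restate the primary objective, and the conclusion that it permits on effectiveness and safety, as a comparison of two strategies.
3. Per-lesion data are already collected, so add only an explicit type label for non-PVI AF lesions, in both arms.
4. Optionally, record before randomization whether the operator intends non-PVI AF ablation if the subject is allocated to control, and specify a supportive comparison among subjects declared PVI-only. Because the declaration precedes allocation, that comparison remains randomized.

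The cost is protocol wording, a lesion-type label and, for the optional step, one further eCRF field and one supportive analysis. The downside is a narrower conclusion if the strategy wording is adopted. The declared PVI-only subset may be small, and lesions prompted by findings during the procedure cannot be fully declared in advance.
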